11 ECONOMIC BURDEN TO PARTICIPANTS

11.1 Financial responsibility for research-related injuries. Answer this question only if the lead researcher is not a UW student, staff member, or faculty member whose primary paid appointment is at the UW.

Describe who will be financially responsible for research-related injuries experienced by subjects, and any limitations. Describe the process (if any) by which participants may obtain treatment/compensation.

The lead researcher is a UW faculty member

11.2 Costs to subjects. Describe any research-related costs for which subjects may be responsible (e.g., CT scan required for research eligibility screening; co-pays; cost of a device).

N/A

11.3 Reimbursement for costs. Describe any costs to subjects that will be reimbursed (such as travel expenses).

N/A

12 RESOURCES

- **12.1** Faculty Advisor. (For researchers who are students, fellows, or post-docs.) Provide the following information about your faculty advisor.
 - Advisor's name
 - Your relationship with your advisor (for example: graduate advisor; course instructor)
 - Your plans for communication/consultation with your advisor about progress, problems, and changes.

N/A

- **12.2 Study team communication**. Describe how you will ensure that each study team member is adequately trained and informed about the research procedures and requirements (including any changes) as well as their research-related duties and functions.
 - There is no study team.

At the beginning of the study the team will meet to discuss the study, deliverables and implementation. Printed study protocols will outline study procedures in detail to ensure proper and consistent implementation. Trainings will be conducted with study staff to ensure they understand the protocols and provide the opportunity to ask questions / give feedback. Weekly team meetings will provide opportunities to discuss any changes in procedures or requirements. Audits of study materials, trackers and databases will take place monthly or quarterly basis with additional training provided if necessary.

13 OTHER APPROVALS, PERMISSIONS, and REGULATORY ISSUES

13.1 Other regulatory approvals. Identify any other regulatory approvals that are required for this research, by checking applicable boxes

Do not attach the approvals unless requested by the IRB.

Approval	Research for which this is required
Radiation Safety	Procedures involving the use of radioactive materials or an ionizing radiation producing machine radiation, if they are conducted for research rather than clinical purposes. Approvals need to be attached to the Supporting Documents page in Zipline .
Institutional Biosafety	Procedures involving the transfer/administration of recombinant DNA, DNA/RNA derived from recombinant DNA, or synthetic DNA.
] _{RDRC}	Procedures involving a radioactive drug or biological product that is not approved by the FDA for the research purpose and that is being used without an IND, for basic science research (not to determine safety and effectiveness, or for immediate therapeutic or diagnosti purposes).
ESCRO	Procedures involving the use of some types of human embryonic stem cells.
example: from a school, extericlinical unit.	dentify any other approvals or permissions that will be obtained. For nal site/organization, funding agency, employee union, UW Medicine
example: from a school, extericlinical unit.	·
example: from a school, extericlinical unit. Do not attach the approvals an	nal site/organization, funding agency, employee union, UW Medicine
example: from a school, externation clinical unit. Do not attach the approvals an We received approval from Utility Financial Conflict of Interest. In this research, as defined by I	nal site/organization, funding agency, employee union, UW Medicine nd permissions unless requested by the IRB. W Medicine Harborview clinic leadership. Does any member of the team have a Financial Conflict of Interest (FCOI
example: from a school, external clinical unit. Do not attach the approvals and We received approval from U' Financial Conflict of Interest. In this research, as defined by I X No Yes If yes, upload the respect to this research, use the	nal site/organization, funding agency, employee union, UW Medicine nd permissions unless requested by the IRB. W Medicine Harborview clinic leadership. Does any member of the team have a Financial Conflict of Interest (FCO

## UNIVERSITY of WASHINGTON

Analytic Approach. Our analyses seek to test the overall effect of our implementation strategies on implementation outcomes (Aim 1), mediators and moderators of those effects (Aim 2), and the impact of the strategies on patient outcomes (Aim 3). In Aim 1, the dependent variables of interest will be penetration and provider acceptability assessed at baseline (prior to initiation of the facilitation strategies), at 3 months (following the completion of the facilitation period), and at 6 months (following 3 months of having no exposure to facilitation). Given the nested data (i.e., time nested within clinicians and clinicians nested within agencies), analyses will rely on 3-level mixed effects regression models. Negative binomial regression with log offsets will be used to model rates, and linear regression will be used to model continuous outcomes. For all models, our independent variables of interest will be a binary indicator of internal versus external facilitation (measured at the organizational level), time, and their interaction. The magnitude and statistical significance of the interaction term will estimate the effect of the implementation strategy on change, or "growth," in outcomes over time. The impact of the intervention strategy on each outcome at each time will also be derived from these models. In addition, we will aggregate facilitylevel data and estimate the average weighted cost metrics across the sample of sites. Future commercial pricing of mHealth technology is unknown, so we will run scenarios that have different ranges of costs for FOCUS and explore the impact on the total program costs.

In Aim 2, mediation will be tested using the product of coefficients approach for multilevel mediation analysis, building on the models in Aim 1. In this approach, the total effect of the implementation strategy is parsed into direct and indirect pathways associated with absorptive capacity, the mediator. Path "a" will represent the effect of the implementation strategy at the organizational level on the clinician-level assessment of absorptive capacity. Path "b" represents the relationship between this mediator and the clinician-level growth parameter, signifying change in outcomes over time. An unbiased estimate of the mediated effect is derived via the product of the "a" and "b" paths (i.e., a\*b) from these analyses. We will test the statistical significance of the mediated effects using the joint significance test and use Monte Carlo simulation methods to derive confidence intervals. Separate mediation models will assess whether absorptive capacity mediates the relationship between implementation strategy and, respectively, penetration, cost, and acceptability outcomes. Moderators of the implementation strategies' effects will be tested by adding terms for each hypothesized moderator and its interaction with the implementation strategy to the Aim 1 models. Specifically, these models will estimate the conditional relationships between the implementation strategies and implementation outcomes across different values of the putative moderators. Organization-level moderators (i.e., Readiness for Change, Organizational Culture, Urban or Rural designation) will be examined. The magnitude of the moderator effects will be probed using simple slopes analysis and region of significance analysis for multilevel models.

In Aim 3, we will use the same techniques as described in Aim 1 to develop 3-level linear mixed regression models that account for the nesting of time within patient and patient within organization to assess the impact of the implementation strategy on patient outcomes over time. We will use the methods described in Aim 2 to examine whether this relationship is moderated by organizational moderators and selected patient demographic characteristics (i.e., gender, race). We will also determine if patients' level of mHealth engagement mediates the relationship between implementation strategy and patient outcomes. All analyses will be conducted using MPlus to

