After receiving interest of a potential participant and consent form has been received researchers would then reach out via phone call to provide a more comprehensive description of the project, screening, and informed consent. Participants will be fully informed that they are free to stop their participation at any time. Candidates will need to pass a brief quiz testing their understanding that participation is completely voluntary. Participants will be required to answer questions demonstrating that they understand what type of data will and will not be collected from them over the upcoming months (self-report and FOCUS use data). Each question will need to be answered correctly before individuals can proceed to provide consent. Individuals who commence the study will be assigned to their sites practice facilitator (external or internal). Randomization will occur at the site level with equal representation of urban and rural settings in each implementation arm.

Staff Participants who will participate in on-site data collection evaluating implementation outcomes and clinic characteristics will be purposively selected from CMHC (both study arms) and from CMHC

administration/budget/finance offices (for costing). The assessment evaluating implementation outcomes will be fully explained to staff participants via webpage (hosted by Qualtrics), where staff can check a box to indicate they are willing to participate. Assessments time points will be at 0M (prior to their patient beginning treatment), then at roughly 3M (time-point after the patient completes treatment). The confidential survey takes 20-30 minutes to complete (questions are included in the supportive documents) and staff will be compensated \$20 in the form of an Amazon gift card for their time. Staff key informants will complete interviews with a trained member of the research team related to costing, including questions about services and effort put towards the study. Key informant interviews will last approximately 60 minutes and be audio-recorded, and later transcribed. Numbers will be provided at aggregate levels, or if treatments were specified, would not identify the individual.

4.2 Recruitment materials.

a. What materials (if any) will you use to recruit and screen subjects?

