The FOCUS application uninstalls at 3 months and then the 3 month web-based outcome assessment will be sent via text and will ask participants to complete it in a private and quiet space. Once again those who express difficulty completing the assessment through the web-based platform can request a call with an assessor on the research team. Participants who complete treatment will be mailed out a certificate of completion to their home address or clinic (based on participant's choice). They will no longer have access to the app, nor will participate in weekly calls for the next 3 months. They would then be sent another assessment at 6 months to complete.

Patient Participant Assessment:

Patient participants will receive a text from researchers just before their assessment date providing instructions on how to complete the online assessment. They will then be invited to conduct assessments at 0, 3, and 6 months via embedded link to a secure study portal (Qualtrics). For participants who need additional assistance, they can come into the participating clinic to complete on a tablet provided by the research team. Patient participants will receive \$30 compensation for each completed assessment (estimated completion time < 45 minutes) for a maximum of \$90 compensation (Plus additional \$10 each assessment to compensate data transmission or travel to site if more assistance is necessary). All participants will be paid for each assessment, but they will not be compensated for engagement in the intervention; assessments are administered to everyone enrolled in the study regardless of how/whether they engaged in FOCUS (note: all patient participants own working smartphones as part of inclusion criteria).

Assessments include questions about psychiatric treatment and hospitalizations, along with other measures of mental health including depression, anxiety, hearing voices, and recovery:

- Demographics and other characteristics
- PhQ9
- GAD-7
- Hospitalization- days hospitalized, no identifiers will be captured.
- ISI: Insomnia Severity Index
- Green Paranoid Thoughts Scale
- Symptom Checklist SCL-9Hamilton Program for Schizophrenia Voices Questionnaire (HPSVQ)
- Recovery Assessment Scale (RAS)
- Illness Management Recovery Scale (IMRS)
- Working Alliance Inventory (3M only)
- mHealth Mastery Measure (3M only)
- AIM
- Satisfaction

Information we plan to collect from EMR data:

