- A list of active participants will be generated either through culling EMR data or talking with clinical teams that will serve as the primary list for their clinical teams to approach to describe the study and gauge interest.
- Services billed- no identifiers will be shared with the research team

Mental Health Provider Participants:

Select mental health providers will be invited to complete an online assessment with the research team. Staff participants will be invited to complete a confidential online survey. This includes exposure to the FOCUS app, if strategies or the program was incorporated into their treatment plans, and perceptions of how the program was adopted and implemented at their clinic.

Mental Health Provider Assessment:

Providers who receive FOCUS data

- Offered mHealth, i.e., the percent of each practitioner's eligible patients who are offered FOCUS
- Treatment Initiation, i.e., percent of consenting patients who followed their practitioner's guidance and went on to download FOCUS onto their smartphone and interact with the system at least once. Dashboard Use, i.e., the average number of times each practitioner logs on to the online FOCUS dashboard to view their individual patients' uploaded FOCUS data

The following will be captured via online confidential** survey (Qualtrics):

- The perception among practitioners that an innovation is agreeable, palatable, or satisfactory. (Measured via AIM / IAM / FIM).
- ORIC: Organizational Readiness for Implementing Change

Providers at the clinic who may not have been directly involved with the FOCUS Intervention (to provide contextual factors) through online confidential survey (Qualtrics):

- Organizational Readiness to Change Assessment (ORCA)
 - CMHC staff participants will complete 23 items using a 5-point bipolar rating scale (1-Strongly agree to 5-Strongly disagree). Constructs evaluated include clinical cooperation within the practice, clarity in patient care goals and process, level of support (e.g., training, budget, staffing) and typical receptivity to guidance (staff) and feedback (leadership).
- Absorptive capacity will be measured among CMHC practitioners who were engaged in IF or EF implementation at 0, 3, and 6 months using the 14-item ACAP Scale.
 - o The ACAP Scale evaluates dimensions of absorptive capacity including
 - Acquiring (e.g., searching for new information, motivation to use information)

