Eligible staff from participating clinics will be asked to complete a confidential survey online prior to their patient starting treatment, then again after their participant completed the intervention (roughly 3 months later).

We would like to request a waiver for the stamp in order to make the form's contact information modifiable (highlighted text in both consent forms).

Costing Interview Key Informants:

Key informants will be selected from selected study sites to complete a costing interview via videoconferencing. Prior to initiating the audio-recorded interview, key informants will review the consent form and provide verbal consent which will be audio-recorded.

c. Comprehension. Describe how you will ensure or test the subjects' understanding of the information during the consent process.

Candidates will need to pass a brief quiz testing their understanding that participation is completely voluntary, how long the research study is and what confidentiality means. Participants will be required to answer questions demonstrating that they understand what type of data will and will not be collected from them.

	cause of the setting or thei	any subject groups that might find it difficult to say "no" to your r relationship with you, even if you don't pressure them to			
Examples: S into their he recruited fr	tudent participants being realthcare provider's resear	recruited into their teacher's research; patients being recruited ch, study team members who are participants; outpatients waiting room just prior to their surgery.			
X No Yes	→ If yes, describe what yo of the setting or relatio	ou will do, for each of these subject groups, to reduce any effect nship on their decision.			
	the researcher will not	dinator will obtain consent instead of the subjects' physician; know which subjects agreed to participate; subjects will have thearing about the study.			
	opportunities (if any) you	volves multiple or continued interaction with subjects over time, will give subjects to ask questions or to change their minds			
documentatio		ch of the statements below describe whether you will obtain uestion does not apply to screening and recruiting procedures uestion 4.6.			
documentation which have alrocumentation obtained by a	n of consent? NOTE: This que ady been addressed in que n of consent that is obtained method that allows verifications.	uestion does not apply to screening and recruiting procedures			

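### The SAP analyses provider acceptability at 6 months, but the protocol's staff survey that carries it is scheduled only at 0 and about 3 months, and the protocol is inconsistent about staff contact at 6 months.

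*SAP*

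**What the plan says.** **SAP, Analytic Approach, Aim 1.** The dependent variables are "penetration and provider acceptability assessed at baseline (prior to initiation of the facilitation strategies), at 3 months", and then "at 6 months (following 3 months of having no exposure to facilitation". The models contain arm, time and their interaction, and the SAP adds: "The impact of the intervention strategy on each outcome at each time will also be derived from these models".

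**Protocol 4.1 (Staff Participants).** For the staff assessment of implementation outcomes: "Assessments time points will be at 0M (prior to their patient beginning treatment), then at roughly 3M (time-point after the patient completes treatment".

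**Protocol 8.2b (Staff Participants).** The consent section repeats the two-wave plan. Staff answer before their patient starts and "then again after their participant completed the intervention (roughly 3 months later".

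**Protocol 5.1 (Mental Health Provider Assessment).** Acceptability is an item of the confidential online staff survey: "The perception among practitioners that an innovation is agreeable, palatable, or satisfactory. (Measured via AIM / IAM / FIM". No time points are attached to it there. Further down the same section, absorptive capacity is to be measured in practitioners engaged in facilitation "at 0, 3, and 6 months using the 14-item ACAP Scale".

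**The concern.** Implementation outcomes are Aim 1 of this hybrid type III trial, and acceptability is one of them. The SAP defines the 6-month point as coming after three months without facilitation, so it is the test of whether any difference between internal and external facilitation in provider acceptability lasts once the facilitator steps back. That effect needs 6-month acceptability data from clinicians, and the documents do not clearly provide for any.

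The gap is by design, so it cannot be repaired at analysis. A wave that was not fielded cannot be recovered later, and the missing-data provision closing the SAP's Analytic Approach is aimed at drop-out. There is also a risk in reporting. Depending on how time is coded, the model may still produce a 6-month estimate, which a reader would take as measured.

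**Working it through.** The point disputes no stated figure, so the check is mainly a comparison of schedules.

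**1. Schedules side by side**

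| Item | Source | 0 | 3 months | 6 months |
|---|---|---|---|---|
| Provider acceptability, as analysed | SAP Aim 1 | yes | yes | yes |
| Staff survey of implementation outcomes | Protocol 4.1 | yes | yes (roughly) | not listed |
| Same survey, consent section | Protocol 8.2b | yes | yes (roughly) | not listed |
| AIM/IAM/FIM in staff | Protocol 5.1 | no times given | no times given | no times given |
| Absorptive capacity in practitioners | Protocol 5.1 | yes | yes | yes |
| Patient assessments | Protocol 5.1 | yes | yes | yes |

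The SAP needs three acceptability waves and the stated staff schedule supplies two. The patient assessment list also contains an AIM, but that is the patients' rating and does not fill the provider gap.

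**2. What the model can give with waves at 0 and 3 months only**

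- *Time as categories.* The 6-month effect is a separate parameter. With no 6-month record in either arm it cannot be estimated.
- *Time as a straight line.* Let D be the between-arm difference in change from 0 to 3 months. The slope difference is D/3 per month, so the fitted 6-month difference in change is 6 × D/3 = 2D, and its standard error is 2 × SE(D). Nothing that happens after month 3 enters this number. This takes the second wave as falling at exactly 3 months. The SAP does not say that time is linear.

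**3. Missing-data method.** Ignorable-likelihood methods use the clinicians who are observed at a wave to inform about those who are not. Here the number observed at 6 months would be 0 of about 100 (20 centres × 5 clinicians, SAP Power Analysis), so there is nothing to borrow from.

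**4. Does the SAP's provider-level detectable effect (d = 0.55) reveal how many waves were intended?** Take 10 centres per arm, 5 clinicians per centre, w waves, two-sided alpha 0.05 and, as an assumption for the provider-level figure, 80% power. The detectable d is then 2.80 × √(2/10 × V), with V = c + p/5 + (1 − c − p)/(5w). Here p = 0.30 is read as the between-provider share and c is a clinic-level ICC that the SAP does not give for provider outcomes.

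- w = 2, c = 0.05 (assumed): V = 0.05 + 0.06 + 0.065 = 0.175, d = 0.524.
- w = 3, c = 0.10 (assumed): V = 0.10 + 0.06 + 0.04 = 0.200, d = 0.560.

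Either number of waves can land near 0.55 with a suitable c, so the power statement does not settle the schedule.

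**The case against.** The best reply is that a 6-month staff contact may well be intended. Section 5.1 is the protocol's procedures section and puts a practitioner scale at 6 months, while the two-wave wording sits in the recruitment and consent answers. The survey forms themselves are not in the documents. This stands, and it means the protocol is inconsistent rather than settled against a 6-month wave. It does not close the gap, because even section 5.1 gives the acceptability scales no 6-month time point. It also lists absorptive capacity under providers who may not have been directly involved with FOCUS, so the same clinicians are not guaranteed.

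A reader might infer more than the documents support:

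- *That staff are never contacted after about 3 months.* The absorptive-capacity schedule contradicts this.
- *That every provider outcome lacks 6-month data.* The components of penetration (patients offered FOCUS, treatment initiation, dashboard log-ons) are listed apart from the survey items, and log-ons need no survey.
- *That dashboard use should be confined to months 0 to 3 because "The FOCUS application uninstalls at 3 months".* Removal is per patient, the SAP expects three patients per provider, and nothing says they start together. Whether 6-month penetration is meaningful is a separate question.
- *That the model will report a doubled effect.* This holds only if time is linear. The SAP's growth language hints at that, but its promise of an effect at each time fits categorical time equally well.
- *That in Aim 2 the mediator cannot precede the outcome.* The SAP relates absorptive capacity to a clinician's growth parameter rather than to a single 3-month score, and the two scales sit under different provider headings. The ordering claim is not established.

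It is also fair to say that the problem touches one later time point of one Aim 1 outcome. The 0 to 3 month acceptability comparison remains estimable, and patient outcomes are scheduled at all three times.

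**Conclusion.** The concern holds for provider acceptability at 6 months. The SAP states an effect for which the documents schedule no data collection, and three protocol statements about staff assessment times do not agree. If sections 4.1 and 8.2b are followed, all of about 100 clinicians lack the 6-month value and persistence of acceptability after facilitation cannot be assessed. Any 6-month figure would be either unavailable (categorical time) or an extrapolation of the 0 to 3 month change (linear time).

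This conclusion assumes that AIM/IAM/FIM are collected only in the staff survey described in sections 4.1 and 8.2b. If the 6-month contact implied by the absorptive-capacity schedule was always meant to carry them, the defect is one of documentation, but it still has to be corrected before that wave falls due.

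**What to change.** Reconcile protocol sections 4.1, 5.1 and 8.2b with SAP Aim 1, in one of two ways.

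1. **Collect the data.** Set the staff schedule to 0, 3 and 6 months in all three protocol sections. State that AIM/IAM/FIM are completed by the same clinicians at the 6-month contact already listed for absorptive capacity. Section 4.1 pays staff $20 for a 20 to 30 minute survey, so the extra cost is at most 100 × $20 = $2,000 for the clinicians in the SAP, or 200 × $20 = $4,000 at the staff maximum in protocol section 2.7. It is less if the 6-month contact is already budgeted. An IRB modification is needed.
2. **Limit the claim.** Restrict the SAP's acceptability model to 0 and 3 months, as a 3-month comparison adjusted for baseline, and say that persistence of acceptability after facilitation will not be assessed. This costs only wording, but gives up the 6-month acceptability question.

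The first is preferable if the wave can still be fielded, because it keeps the question the SAP set out to answer. Under either option the SAP should state whether time enters as categories or as a line.

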## UNIVERSITY of WASHINGTON

appropriately estimate multilevel regression models and to conduct Monte Carlo simulations. Our multilevel models in MPlus will allow us to accommodate likelihood-based ignorable analyses to obtain unbiased model inference without directly modeling drop-out associated with attrition.

Power Analysis. The sample size for the project is limited by the maximum number of organizations and clinicians that can be recruited within the logistical and financial constraints of an R01. With our available resources, we expect to enroll 20 CMHCs, with 5 clinicians per CMHC, and 3 patients per provider (n=300 patients, 100 providers). Based on our prior work (see Pilot Study B), we were able to calculate a between-organization ICC of 0.19 and a between-patient ICC of 0.45 for patientlevel outcomes similar to those being tested in this study. With an average of 15 patients per site, we will have 80% power to detect small to moderate effects of the implementation strategy on patient outcomes (Cohen's d=0.44). For provider-level outcomes, assuming a between-provider ICC of 0.30, we will have power to detect moderate effects of the implementation strategy (Cohen's d=0.55). Alpha is set at .05 (two-tailed) and will not be adjusted for multiple comparisons because we prefer to explore leads that may turn out to be wrong rather than miss potentially important findings. Using similar model assumptions, the study will have sufficient power to detect moderate effects of organizational-level moderators on patient outcomes (Cohen's d=0.50) and provider outcomes (Cohen's d=0.61). For the mediation analysis, the proposed sample size will yield sufficient power to detect a large indirect effect (Cohen's d=0.85) of the strategy through the practitioner-level mediators and a large indirect effect (Cohen's d=0.65) of the strategy through the patient-level mediators, assuming there is a moderate effect of the implementation strategy.

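### If treatment initiation or offers of FOCUS are fitted as negative binomial rates with model-based standard errors, the single-time IF v EF contrast is too imprecise at high uptake; the SAP should name a method suited to k-of-n proportions

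*SAP*

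**What the plan says.** **SAP, Analytic Approach, Aim 1.** Penetration and provider acceptability are analysed in 3-level mixed models (time within clinician within agency). On model choice: "Negative binomial regression with log offsets will be used to model rates, and linear regression will be used to model continuous outcomes". No logistic, binomial or beta-binomial model appears in the SAP. The main term is the strategy-by-time interaction, but "The impact of the intervention strategy on each outcome at each time will also be derived from these models". On software, the sentence begins "All analyses will be conducted using MPlus to" and goes on to multilevel estimation. It does not say whether standard errors are model-based or robust.

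**Protocol section 5.1, Mental Health Provider Assessment.** Three usage measures fit the penetration outcome:
- *Offered*: the percent of each practitioner's "eligible patients who are offered FOCUS".
- *Treatment initiation*: the "percent of consenting patients who followed their" practitioner's advice and went on to "download FOCUS onto their smartphone and interact with the system at least once".
- *Dashboard use*: an average number of log-ons, which is a count.

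**SAP, Power Analysis.** The planned size is "20 CMHCs, with 5 clinicians per CMHC, and 3 patients per provider", that is 15 patients per site and 300 in all. A between-organization ICC of 0.19 is given for patient-level outcomes. No ICC is given for initiation.

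**The concern.** *Offered* and *initiation* have a ceiling: no more than n of n patients can be offered or can start. With mean np, a binomial count has variance np(1−p). A Poisson count has variance np, and a negative binomial count has more than that. At 90% uptake the binomial variance is one tenth of the Poisson variance. Neither the negative binomial dispersion nor a random intercept can go negative to make up the gap. Variation between sites adds real spread and closes part of it, but at high uptake and modest ICC it does not close all of it.

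High uptake is what the nearest pilot figures suggest. Protocol section 1.8b reports 90% commencement with external facilitation (part C) and 92% of those offered FOCUS agreeing to use it with internal facilitation (part D). At stake is the IF v EF comparison on initiation. A real difference could be missed, or the interval could be too wide to support a statement that the two models perform alike. This also sits badly with the SAP's stated reason for leaving alpha unadjusted, which is that it would rather follow false leads than miss findings.

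**Working it through.** **The plan's own figure.** The SAP states 80% power at d = 0.44 for patient outcomes. Take 150 per arm, a design effect of 1 + 14×0.19 = 3.66, and an inferred factor for baseline adjustment with two follow-ups, (1+0.45)/2 − 0.45² = 0.5225. The detectable d is then 0.447 and power at 0.44 is 79%, so the stated figure reproduces. The SAP gives no figure for initiation.

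**Inputs.** 15 patients per site and ICC 0.19 (SAP, Power Analysis). Assumed: 10 sites per arm, equal site sizes, the uptake rates, and that 0.19 applies to initiation.

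**Formulas for the log ratio at one time point**, with D = 1 + 14×ICC:
- True variance = sum over arms of (1−p)D/(150p).
- Model variance = sum over arms of max[15p, 15p(1−p)D] / [(15p)²×10]. The first term in the max is the Poisson floor.

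**90% v 90%, ICC 0.19.**
- True SE = √(2×0.1×3.66/135) = 0.074.
- Model SE = √(2/135) = 0.122. Ratio 1.65.
- If the observed ratio is 1, the model-based 95% interval is exp(±1.96×0.122), or 0.79 to 1.27. A valid one with t on 18 df is exp(±2.101×0.0736), or 0.86 to 1.17.

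**90% v 80%, ICC 0.19.**
- True SE = √[3.66×(0.111+0.250)/150] = 0.094.
- Model SE = √[(1.111+1.250)/150] = 0.125. Ratio 1.34.

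**SE ratio (model ÷ true) by formula:**

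| Uptake | ICC 0 | 0.05 | 0.10 | 0.19 | 0.30 |
|---|---|---|---|---|---|
| 90% v 90% | 3.16 | 2.43 | 2.04 | 1.65 | 1.39 |
| 90% v 80% | 2.56 | 1.96 | 1.65 | 1.34 | 1.13 |
| 80% v 80% | 2.24 | 1.71 | 1.44 | 1.17 | 1.00 |
| 80% v 70% | 1.99 | 1.52 | 1.28 | 1.07 | 1.00 |
| 70% v 70% | 1.83 | 1.40 | 1.18 | 1.00 | 1.00 |

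The two spreads meet where (1−p)D = 1: ICC 0.64 at 90%, 0.29 at 80% and 0.17 at 70%.

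**Simulation at ICC 0.19** (beta-binomial site clustering, log-link model with a site random intercept). The model SE divided by the observed spread was:
- 1.62 to 1.65 at 90% v 90%
- 1.27 to 1.29 at 90% v 80%
- 1.10 to 1.17 at 80% v 80%
- 1.06 at 80% v 70%
- 1.00 at 70% v 70%
- 0.96 at 60% v 50%

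The estimated negative binomial dispersion was essentially zero, so the fit reduces to a Poisson mixed model.

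**Rejection rates at ICC 0.19:**

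| Uptake | Model-based | Site-level t-test | Robust log-link, t on 18 df |
|---|---|---|---|
| 90% v 90% (null) | 0.4% | 4.2% | 3.2% |
| 80% v 80% (null) | 2.3% | 5.4% | 3.7% |
| 90% v 80% | 8–10% | 20–25% | 20% |
| 90% v 70% | 46–48% | 61–62% | 55% |
| 80% v 70% | 16% | 18% | 14% |
| 70% v 55% | 32% | 28% | 24% |

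At 50% in both arms, null rejection with the model-based fit was about 7% at ICC 0.19 and 8.5% at ICC 0.30.

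**The case against.** The strongest objection is that the SAP does not prescribe this analysis. It does not say that initiation is one of its rates, and it does not say that standard errors are model-based; site-robust standard errors would remove the excess width. This stands. A reader might infer that the SAP has specified a wrong analysis for initiation. The documents support only that its sole model for rates would misbehave here under one open choice, and that the choice is left open.

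Four further limits also stand.
- **Not the main Aim 1 term.** A reader might carry the factor of 1.6 over to the strategy-by-time interaction. The SAP's baseline precedes facilitation, and Protocol section 5.1 has patients install the app with the facilitator after the baseline assessment. Initiation therefore has no pre-facilitation value, and the figures cover only the single-time contrast.
- **Borrowed inputs.** The ICC of 0.19 belongs to patient outcomes. The pilot 90% and 92% come from differently run programmes, and the 92% is agreement among those offered, not initiation among those who consented. For *Offered*, the documents give no expected rate and no number of eligible patients per clinician.
- **Not conservative everywhere.** A reader might infer that false positives are never in excess. That holds at high uptake only; near 50% the model-based standard error is slightly too small.
- **Power is limited anyway.** At 90% v 80%, a valid analysis still has only about 20 to 25%.

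What does not stand is that silence makes the point harmless. With only two model families named, following the stated rule for rates leads to this analysis.

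**Conclusion.** The point holds in conditional form. If *initiation* or *Offered* is analysed as a rate by negative binomial regression with model-based standard errors, the single-time IF v EF contrast is too imprecise when uptake is high. For initiation at ICC 0.19 the factor is about 1.6 at 90% v 90%, 1.3 at 90% v 80%, 1.1 to 1.2 at 80% v 80%, and about 1.0 or slightly below at 70% and under. A smaller ICC makes it worse and extends it to lower uptake; a larger one shrinks it. *Offered* is affected in the same way only if the offer rate is high. Dashboard log-ons are counts and are not affected.

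The result rests on 10 equal sites per arm, 15 patients per site, one time point, a borrowed ICC and assumed uptake. Severity is minor to should-fix: the error is conservative in the range where it is large, and the remedy is cheap.

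**What to change.** State in the SAP the model and standard-error type for each penetration measure. Do not use negative binomial with model-based standard errors for *initiation* or *Offered*. Pre-specify one main method that respects the k-of-n form and is valid with 20 sites. Any of these would serve:
- a site-level comparison of proportions with a t reference (about 18 df);
- a log-link model with site-clustered robust standard errors and a t reference, if a ratio is wanted;
- a binomial mixed model with a small-sample correction. An uncorrected Wald test rejects about 9 to 12% under the null at ICC 0.19, and t on 18 df corrects this only in part (7 to 10%).

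Nothing here requires the site-level test or a risk difference in particular; the choice is the sponsor's. Keep negative binomial with a log offset for dashboard log-ons.

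The cost is SAP wording and a little more analysis work, with no new data. The effect measure may change. The robust log-link option gives up some power at lower uptake (24% against 28% for the site-level test at 70% v 55%).
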